9.2.1.7 TCS with EAACI medication scoring (TCSEAACI)

The TCS with EAACI medication scoring (TCSEAACI) is the sum of DSS/6 and DMSEAACI and ranges from 0 to 5.

9.2.2 Derivation of average symptom and medication scores

9.2.2.1 Average Daily Rhinoconjunctivitis Symptom Score (average DSS)

The average DSS during a given pollen season is the mean of all non-missing DSS over all days in the selected pollen season. Average DSS will be derived for the BPS, TPS, AHPS, OPS [REDACTED]

9.2.2.2 Average Daily Rhinoconjunctivitis Medication Score (average DMS)

The average DMS during a given pollen season is the mean of all non-missing DMS over all days in the selected pollen season. Average DMS will be derived for the BPS, TPS, AHPS, OPS [REDACTED]

9.2.2.3 Average Daily Rhinoconjunctivitis Total Combined score (average TCS)

The average TCS during a given pollen season is the mean of all non-missing daily TCS over all days in the selected pollen season. Average TCS will be derived for the BPS, TPS, AHPS, OPS [REDACTED] The definitions of the pollen seasons are provided in section 9.1.

[REDACTED]
[REDACTED]
[REDACTED]
[REDACTED]

9.2.2.5 Average Daily Total Combined Score with EAACI medication scoring (average TCSEAACI)

The average TCS (EAACI scoring) is the mean of the daily non-missing values of the AR/C daily TCS with EAACI scoring.

The average TCS (EAACI scoring) will be derived in the BPS and TPS.

9.2.3 Derivation of daily binary variables

9.2.3.1 Proportion of well days

A well day is defined as a day with no use of AR/C rescue medication (i.e., DMS=0) and DSS less than or equal to 2. A day that meets the definition of well day will take the value 1, and 0 otherwise.

The proportion of well days during BPS and TPS is the number of well days/total number of days in a season (BPS or TPS).

9.2.3.2 Proportion of severe days

[figure not shown]
A severe day is a day with a DSS greater than or equal to 6 and at least 2 moderate symptoms or 1 severe symptom. A day that meets the definition of severe day will take the value 1, and 0 otherwise.

The proportion of severe days during BPS and TPS is the number of severe days/total number of days in a season (BPS or TPS).

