6.6 Additional endpoints analyses

6.7 Secondary endpoints

The following secondary endpoints will be analysed identically to the primary endpoint using the main estimator for the trial product estimand:

- Average TCS during the AHPS and OPS
- Average DSS during the AHPS and OPS
- Average DMS during the AHPS and OPS
- Average TCS (EAACI scoring) during BPS and TPS

Following endpoints will be analysed under the hypothetical strategy using the same intercurrent events and imputation approach defined for the main estimator.

- Proportion of severe days during BPS and TPS
- Proportion of well days during BPS and TPS
- Proportion of symptom-free days during BPS and TPS

The proportion of severe days during BPS will be analysed using a GLMM with a logit link function. For the proportion of severe days during BPS the model will include “number of severe days/total number of days in BPS” as the response variable and treatment, cohort and age group as fixed effects and pollen station within cohort as random effects. From the GLMM model, the odds ratio of having a severe day of active treatment relative to placebo will be presented together with the corresponding p-values and 95% confidence limits. The endpoints proportion of severe days during TPS, proportion of well days during BPS and TPS, and symptom-free days during BPS and TPS will be analysed using the same model as for severe days during BPS. The imputation of missing data of aforementioned endpoints, will be done by using unrestricted random sampling method, which utilises selection with equal probability and with replacement. For each subject with missing data, the number of days in pollen season as well as the number of days with the endpoint of interest will be replaced from the pool of completed subjects with non-missing data in the same age group and the treatment group according to hypothetical strategy.

A plot with the results from the statistical analyses of the endpoints proportion of severe days, proportion of well days and proportion of symptom-free days during BPS will be presented. The plot will include estimated proportions of having a severe day, well day and symptom free days, the relative difference including 95% CI, and a p-values.

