6.9.1.3 IMP compliance

IMP compliance (%) will be calculated for each subject as number of tablets taken divided by the treatment duration (days) multiplied by 100.

IMP compliance (%) will be summarised by treatment group.

Percentage IMP compliance will be summarised by treatment group.

6.9.1.4 eDiary compliance

eDiary compliance (%) for the TPS will be calculated as the number of non-missing eDiary entries in the TPS divided by total number of days in the TPS.

eDiary compliance (%) will be summarised by treatment group.

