9.2.3.3 Proportion of symptom-free days

A symptom-free day is defined as a day with no symptoms and with no use of rescue medication (i.e., daily TCS=0). A day that meets the definition of symptom-free day will take the value 1, and 0 otherwise.

The proportion of symptom-free days during BPS and TPS is the number of symptom-free days/total number of days in a season (BPS or TPS).

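### Severe-, well- and symptom-free-day proportions are divided by all season days, so days without diary data count as non-events, and the sample code uses a denominator that is never defined

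*SAP*

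**What the plan says.** SAP 9.2.3.2 defines the proportion of severe days as a quantity that "is the number of severe days/total number of days in a season (BPS or TPS"), and adds: "A day that meets the definition of severe day will take the value 1, and 0 otherwise". For well days, 9.2.3.1 has the same denominator: the proportion "is the number of well days/total number of days in a season (BPS or TPS"). For symptom-free days, 9.2.3.3 repeats both the denominator and the coding: "A day that meets the definition of symptom-free day will take the value 1, and 0 otherwise". SAP 6.7 carries the rule into the logistic mixed model, whose response is "number of severe days/total number of days in BPS".

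Three other places bear on the meaning:

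- The averaged scores in 9.2.2 use observed days only. Average TCS, for example, "is the mean of all non-missing daily TCS over all days in the selected pollen season".
- eDiary compliance (SAP 6.9.1.4) is "the number of non-missing eDiary entries in the TPS divided by total number of days in the TPS".
- The sample code in Appendix C, Table 12, models `aval / datadays`. Neither document defines `datadays`.

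On imputation, SAP 6.7 says that, where data are missing, "the number of days in pollen season as well as the number of days with the endpoint of interest will be replaced", both counts being taken over from a donor. It does not say whether a partly completed season makes a subject one with missing data. These endpoints are analysed under the hypothetical strategy, for which SAP 5 (DPS1) removes everything collected after treatment discontinuation.

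**The concern.** Under the written rule, a day on which nothing is known is scored as not severe, not well and not symptom-free. Every proportion is then the rate on observed days multiplied by diary completeness. If completeness is the same in both arms, the treatment effect is slightly attenuated. If it differs, the difference in completeness enters the odds ratio as if it were a treatment effect. The direction also varies by endpoint: poorer completeness flatters an arm on severe days and penalises it on well and symptom-free days.

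Treatment discontinuation makes this sharper. A subject who stops mid-season after some diary days could keep all later season days in the denominator as non-events. That does not represent the estimand, which asks what would have happened had treatment continued.

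A programmer who follows the text and one who reads `datadays` as days with data would report different odds ratios, p-values and confidence limits from the same data.

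**Working it through.** **Reading the text.** The compliance definition in 6.9.1.4 sets non-missing entries against the total number of season days, so the SAP itself treats these as two different counts. Nothing in 6.7 or 9.2.3 exempts an undiarised day from the denominator or from the 0 code.

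**Does imputation repair it?** SAP 6.7 adopts the main estimator's approach, which imputes only when the endpoint is missing. Protocol 15.15 derives a season average from as little as one diary entry and does not impute single missing days for the main estimators. If the proportions follow that rule, partial seasons are not imputed and the problem remains.

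**Formulas.** Let p be the event rate on observed days and c the diary completeness.

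- Proportion as written = p × c
- OR(a, b) = [a/(1−a)] / [b/(1−b)], active over placebo

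This is arithmetic on pooled proportions, without the model's covariates or station effect. All values of p and c are assumptions. The documents give only a target of at least 80% daily diary compliance (protocol 14.2).

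**Equal completeness in both arms.** Assumed rates, active v placebo: severe days 15% v 20%, well days 40% v 30%.

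| Completeness | Severe-day OR | Well-day OR |
|---|---|---|
| Observed days | OR(0.15, 0.20) = 0.706 | OR(0.40, 0.30) = 1.556 |
| 95% | 0.708 | 1.538 |
| 80% | OR(0.12, 0.16) = 0.716 | OR(0.32, 0.24) = 1.490 |
| 70% | 0.721 | 1.463 |

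**Unequal completeness, no true effect.** Assumed rates: severe 20% and well 30% in both arms, so the correct OR is 1.

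| Active v placebo completeness | Severe-day OR | Well-day OR |
|---|---|---|
| 90% v 95% | OR(0.18, 0.19) = 0.936 | OR(0.27, 0.285) = 0.928 |
| 80% v 85% | OR(0.16, 0.17) = 0.930 | OR(0.24, 0.255) = 0.923 |
| 70% v 95% | OR(0.14, 0.19) = 0.694 | OR(0.21, 0.285) = 0.667 |

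The direction follows the less complete arm. With a 40% rate in both arms, 75% v 85% gives OR(0.30, 0.34) = 0.832, and 85% v 75% gives 1.202.

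**One subject.** In SAP Appendix D, the cohort 2 birch season at PLLODZ runs from 16-04-2023 to 06-05-2023, which is 15 + 6 = 21 days. Suppose a subject stops treatment after day 7 with a complete diary to that point and 4 severe days. As written, and if the partial season is not imputed, the score is 4/21 = 19.0%. On observed days it is 4/7 = 57.1%.

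**The case against.** The best counter-argument is that the literal reading is not the intended one. The daily indicators are built from DSS and DMS, which do not exist on a day without an entry, so the 0 code may be meant only for observed days. Protocol 15.15 declines to impute missing diary days, and scoring a blank day as a non-event is in effect imputation. The name `datadays` suggests days with data. A subject who stops mid-season may count as one with missing data and have both counts replaced, so the PLLODZ example needs the unfavourable reading of two rules at once. A 25-point completeness gap is also unlikely in a double-blind trial where sites are alerted to missed entries. Finally, a mean over observed days and a proportion of season days need not share a denominator.

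Much of this is fair on size. The 70% v 95% row is an outer bound and should carry little weight, and the single-subject example is conditional. It does not settle the definition. The diary-day reading rests on inference from a variable name and from a protocol paragraph about averaged endpoints, whereas four SAP sections state the season-day denominator and 6.9.1.4 shows what that phrase means in this SAP. If diary days were intended, the text is wrong and needs correcting.

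**Conclusion.** The concern holds. As written, the three proportions count undiarised and excluded days as non-events, which is inconsistent with the averaged scores, and the sample code does not identify the denominator. That `datadays` means days with data is plausible but not stated.

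Under the assumed rates, equal completeness of 70% to 95% changes the odds ratios only mildly. A 5-point gap between arms produces a spurious odds ratio of about 0.92 to 0.94, or the reverse if placebo is the less complete arm. Actual completeness by arm is not in the documents, so the real size is unknown.

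The consequence is limited. SAP 4.1.1 leaves these endpoints outside multiplicity control, so neither the type I error rate nor the primary and key secondary results are touched. They will nevertheless be reported with p-values and confidence limits, and the BPS results with a dedicated plot, so the analysis should be uniquely defined. This should be corrected, but it does not threaten the trial's main conclusion.

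**What to change.** - In SAP 6.7 and 9.2.3.1 to 9.2.3.3, define the denominator as the subject's days in the season with a non-missing diary entry in the applicable data point set, and classify only those days as 1 or 0.
- Under Table 12, define `datadays` as exactly that count.
- In 6.7, state that donor imputation applies when the subject has no such day in the season, in line with the averaged endpoints.

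This denominator still relies on unobserved days being ignorable, as the averaged scores already do; protocol 15.15 makes that assumption for occasional missing entries.

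The cost is wording in four SAP sections and one definition in Appendix C. It needs no new data and no change of model. If the SAP can no longer be amended, the denominator actually used should be documented in the clinical trial report, as protocol section 15 requires for changes from the final SAP.

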9.2.3.3 Proportion of symptom-free days

A symptom-free day is defined as a day with no symptoms and with no use of rescue medication (i.e., daily TCS=0). A day that meets the definition of symptom-free day will take the value 1, and 0 otherwise.

The proportion of symptom-free days during BPS and TPS is the number of symptom-free days/total number of days in a season (BPS or TPS).

9.2.4 Other derivations of endpoints

9.2.4.1 RQLQ

The RQLQ(S) consists of 28 items covering 7 domains (activities, sleep, no-nose/eye symptoms, practical problems, nasal symptoms, eye symptoms, emotional). Each item is scored on a 7-point (0-6) scale, where lower scores indicate better quality of life and all items within each domain are weighted equally. The domain scores are derived as the mean of all item scores within each domain. The overall RQLQ score is the mean of the 28 item scores.

The RQLQ(S) is completed weekly in the eDiary during TPS by subjects aged 12-17 years at randomisation.

9.2.4.2 PRQLQ

The PRQLQ consists of 23 items covering 5 domains (nasal symptoms, eye symptoms, practical problems, activity limitation and other symptoms). Each item is scored on a 7-point (0-6) scale, where lower scores indicate better quality of life and all items within each domain are weighted equally. The domain scores are derived as the mean of all item scores within each domain. The overall PRQLQ score is the mean of the 23 item scores.

The PRQLQ is completed once during the BPS by subjects aged 5-11 years at randomisation.

9.2.4.3 TSQM-9

The TSQM-9 consists of 9 items covering 3 domains (Effectiveness, Convenience, Global satisfaction). Items are scored on either a 5-point (1-5) scale or 7-point (1-7) scale, where higher scores indicate greater treatment satisfaction. For each domain, item scores are summed and normalised to a 0-100 scale, where 0 is the worst possible level of satisfaction and 100 is the best possible level of satisfaction. The calculations specific to each domain are presented in detail in the Treatment Satisfaction Questionnaire for Medication (TSQM) User Manual, version 1.8, 08Jun2020.

9.2.4.4 Patient-rated global evaluation of treatment efficacy

Subjects will be asked the following question regarding their perception of the efficacy of the treatment they received during the birch/tree pollen season: “Compared to your rhinitis and/or conjunctivitis symptoms in the previous birch/tree pollen season, how have you felt overall in this birch/tree pollen season?”

Subjects will respond to the question using the 5-point scale: much better, better, the same, worse, much worse.

‘Better’ or “much better” will be categorised as “improved”, and “much worse”, “worse” or “the same” will be categorised as “not-improved”.

9.2.4.5 Lung function

Measurements of FVC, FVC percent predicted, FEV1 and FEV1 percent predicted will be recorded by the trial sites. The formulae used for calculating predicted FVC and predicted FEV1 can vary slightly depending on the spirometer used at each site. Therefore, for reporting purposes, FVC percent predicted and FEV1 percent predicted will be recalculated using values of predicted FVC and predicted FEV1 calculated from the Quanjer equations (Quanjer et al. 1995). This is to ensure a standard approach to the derivation of the endpoints. The Quanjer formulae for predicted FVC and FEV1 are a function of age, height, and race.

9.2.5 Imputation of dates

9.2.5.1 Partial dates in adverse event reporting

Partial dates and time for **start** of AEs are handled in the following way:

- Missing day is imputed as maximum of first day of month and day of first IMP
- Missing month is imputed as maximum of first day in January and date of first IMP

Partial dates and time for **end** of AEs are handled in the following way:

- Missing day is imputed as minimum of last day in month and day of last contact
- Missing month is imputed as minimum last day of December and date of last contact

With these imputation rules, AEs are considered treatment emergent when dates are partial, and the existing information does not exclude the possibility of the event being treatment emergent.

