12 SAFETY PROCEDURES

Information about AEs, whether reported by the subject, discovered by the investigator by reviewing eDiary records, detected through physical examination, laboratory test or other means, must be collected and recorded on the AE form and followed up as appropriate. Evaluation of AEs including severity, causality, outcome and seriousness assessments must be performed by a physician.

Any AE occurring from the time the informed consent is signed by the subject and until the last follow-up phone contact must be recorded and reported on the AE page in the eCRF. This includes all AEs, even AEs occurring before the subject is administered the IMP and whether or not AEs are observed in connection with the trial assessments and conduct of the trial.

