Date of last contact	Date of the last contact, either by telephone or in a visit.
End of trial	The overall end of the trial is defined as the date of last follow-up phone visit (TC4) for the last subject in the trial globally.
Estimand	A precise description of the treatment effect reflecting the clinical question of interest posed by the trial objective. It summarises at a population-level what the outcomes would be in the same patients under different treatment conditions being compared (ICH 2020).
ESI	ESIs are selected AEs that are considered critical for the evaluation of the product's safety profile and for which additional data will be collected.
IMP	A pharmaceutical form of an active substance or placebo being tested or used as a reference in a clinical trial, including products already with a marketing authorisation but used or assembled (formulated or packaged) in a way different from the authorised form, or when used for an unauthorised indication, or when used to gain further information about the authorised form.
IE	Events occurring after treatment initiation that affect either the interpretation or existence of the measurements associated with the clinical question of interest. It is necessary to address IEs when describing the clinical question of interest in order to precisely define the treatment effect that is to be estimated (ICH 2020).
IRT	Automated system that can be used for managing randomisation, subject enrolment, and trial supply management in a clinical trial.
Rescue medication	Medicinal products provided by ALK when the efficacy of the IMP is not sufficient or likely to cause an adverse event to the subject or to manage an emergency situation in relation to allergy symptoms in agreement with the EMA Definition of IMPs and use of AMPs

consultation document (EMA 2016).

TEAEs	An adverse event with start date on or after the time of first IMP administration and no later than 7 days after last IMP administration.
Trial discontinuation date	Date of subject trial discontinuation. In case of subjects lost to follow-up, the trial discontinuation date is defined as the date the investigator/sponsor decides to discontinue the subject from the trial.

3 Introduction

The statistical analysis plan is a supplement to the statistical section in the CTP and provides additional details regarding estimands (where applicable), analysis sets, endpoints, and the statistical analyses.

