6.9.2.2 Reporting of adverse events

AE is considered a TEAE if the time of onset is after the time of first dose of IMP and at most 7 days after last dose of IMP.

All TEAEs will be summarised by treatment group according to causality, severity (mild, moderate, severe), seriousness, action taken, outcome, and whether the event led to IMP discontinuation. The number of subjects in each treatment group, the number and frequency of

subjects having the event, as well as the number of events and proportion of events will be displayed. A similar summary table will be produced for all IMP-related TEAEs.

All TEAEs and all IMP-related TEAEs will be summarised (in separate tables) by treatment group, SOC, and PT, displaying number of subjects in treatment group, and number and frequency of subjects having the event. The tables will be sorted according to most frequent SOC and PT in the active treatment group, and the most common TEAEs (preferred term from MedDRA) defined as those that are present in at least 5% of subjects in the active treatment group will be marked.

Severe TEAEs will be listed only, if there are fewer than 10 events in total. Otherwise, severe TEAEs will also be summarised similar to how TEAEs are presented. The same applies for SAEs, IMP-related SAEs, TEAEs leading to IMP interruption, and TEAEs leading to IMP discontinuation.

For most frequent IMP-related TEAEs (present in at least 5% of subject in the active treatment group) onset and duration will be presented as follows: Average time to onset and average duration both in days, will be presented by PT and treatment. In addition, for day 1 of treatment average time to onset in day and minutes will be presented by SOC, PT, and treatment.

For the most frequent IMP-related TEAEs which are recurrent, the average daily duration and the average duration in days from first to last occurrence will be presented by SOC, PT and treatment.

Most frequent non-serious TEAEs in any arm (≥ 1 and $\geq 5\%$) will be summarised by system organ class and preferred term.

A table with the overall summary of the safety profile will be produced showing subjects with TEAEs, IMP-related TEAEs, IMP-related severe TEAEs, IMP-related treatment-emergent SAEs, IMP-related TEAEs leading to IMP discontinuation, and each type of IMP-related treatment-emergent ESI by treatment group.

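### Read literally, the partial-date rule moves AEs from months known to precede treatment onto the first-dose date, and the SAP's two TEAE definitions disagree at that boundary

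*SAP*

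**What the plan says.** SAP section 9.2.5.1 has two rules for an incomplete AE start date. For a missing day: "Missing day is imputed as maximum of first day of month and day of first IMP". For a missing month: "Missing month is imputed as maximum of first day in January and date of first IMP". Neither carries a condition on which month or year the event belongs to. The section closes with the principle behind the rules: a partial-date AE is treated as emergent when "the existing information does not exclude the possibility of the event being treatment emergent". The start rules are introduced as covering dates and times, but no rule is given for a missing time.

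Treatment emergence is defined twice in the SAP. The list of definitions (section 2) has "An adverse event with start date on or after the time of first IMP administration", which matches the protocol's table of definitions. Section 6.9.2.2 has "AE is considered a TEAE if the time of onset is after the time of first dose of IMP". Section 6.11, which lists departures from the protocol, does not mention this difference.

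The protocol collects events from well before dosing. Section 12 covers "Any AE occurring from the time the informed consent is signed by the subject" and says explicitly that events before the first IMP dose are included. Table 6 puts screening 1 to 26 weeks before randomisation, and protocol section 9.2 allows the first dose to be postponed.

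**The concern.** A maximum with no condition does the right thing in the month of first dose and in later months. In earlier months it does not: the first of the month always precedes the first dose, so the maximum always returns the first-dose date. An event whose recorded month already shows it was not treatment emergent is then moved onto the first day of treatment. That contradicts the sentence that explains the rule, and it can put the start of an event after its end.

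The two TEAE definitions compound this, because the rule places events exactly on the boundary where they differ. This includes the events the rule is meant to capture: those known to fall in the month of first dose, day unknown.

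At stake is the TEAE flag. Under SAP section 6.9.2.2, TEAEs are tabulated, while non-emergent events are only listed. Some tables depend on low counts: severe TEAEs and SAEs, for example, are listed only if there are fewer than 10 events.

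**Working it through.** The plan gives no figure to reproduce. The check applies the rule as written to example dates and compares the result with the closing principle and with both TEAE definitions.

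**Input.** First dose 20-Oct-2022, assumed for illustration. It lies within cohort 2's randomisation period (SAP Table 3), and July 2022 lies within 26 weeks before it.

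**Formula.** Imputed start = max(first day of AE month, date of first IMP).

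| AE recorded as | Imputed start | Known month excludes emergence? | SAP section 2 and protocol | SAP 6.9.2.2 |
|---|---|---|---|---|
| Jul-2022 | 20-Oct-2022 | yes | TEAE | tie, not settled |
| Sep-2022 | 20-Oct-2022 | yes | TEAE | tie, not settled |
| Oct-2022 | 20-Oct-2022 | no | TEAE | tie, not settled |
| Nov-2022 | 01-Nov-2022 | no | TEAE | TEAE |

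The first two rows conflict with the closing principle. The third is the case the rule exists for. Under 6.9.2.2 it is excluded if the event takes the first-dose time, and cannot be classified if it carries no time.

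**Start after end.** If the July event's end date is also known only as July 2022, the end-date rule gives 31-Jul-2022. The imputed start is then 31 (August) + 30 (September) + 20 (October) = 81 days after the end.

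**Alternative reading.** Suppose the day of first IMP means the day number, 20. July becomes 20-Jul-2022 and stays pre-treatment. But November becomes 20-Nov-2022, which is 20 − 1 = 19 days after the first of the month. With an assumed last dose of 05-Jun-2023, an event recorded as June 2023 becomes 20-Jun-2023. That is 15 days after last dose and outside the 7-day window, although the known month does not exclude emergence. The parallel missing-month rule refers to the date of first IMP, which favours the calendar-date reading. Neither reading satisfies the closing principle in all months.

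**Year-only dates.** The missing-month rule errs in the same way only if the AE year precedes the first-dose year. In Table 3, first visit and last randomisation fall in one calendar year for each cohort (08-Apr-2021 to 01-Nov-2021; 10-Mar-2022 to 21-Dec-2022). This branch would need a first dose postponed into the next year.

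**How often a pre-dose day falls in an earlier month.** As an illustration, with every first-dose date in 2021 weighted equally, the share of pre-dose days lying in an earlier calendar month is 13.2% for 1 week of screening, 47.7% for 4 weeks, 82.5% for 12 weeks and 91.9% for 26 weeks. With longer screening, then, most pre-dose partial dates would meet the faulty branch. How many such dates exist cannot be read from the documents.

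**The case against.** The closing sentence of 9.2.5.1 states the intended result. Read as a whole, the section lacks only a few words limiting the maximum to the month of first IMP, and a programmer guided by that sentence would not flag a July event. This stands as evidence of intent. It does not remove the conflict, because the bullets are the operative rule and give the opposite answer.

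A reader might infer that the onset, duration and day-1 tables would be wrong. The documents do not support that. SAP 6.9.2.2 limits those tables to IMP-related TEAEs present in at least 5% of active subjects. Relatedness is the investigator's causal judgement (protocol section 12.2.2), and an event from a month before the first tablet should not be judged possibly caused by it. Such events should rarely enter those tables.

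A reader might also infer that 6.9.2.2 would drop the immediate local reactions typical of this product. It would not. Those reactions follow the supervised first intake, so their onset is after the dose and both definitions count them. The definitions part only when onset is timed at the dose or has no recorded time.

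The size objection is fair as well. AEs are assessed at V1, at TC1 where held, and at V2, and omissions in the eCRF raise queries, both of which should keep partial dates few.

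**Conclusion.** The rule is wrong as written: followed literally, it gives a TEAE flag that the section's own principle forbids. The disagreement between 6.9.2.2 and the other two definitions is a plain inconsistency, and it also leaves same-month partial dates without a settled status.

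The consequence is limited to the all-TEAE counts and the tables built on them. The number of events is unknown. It is probably small, on the assumption that site follow-up leaves few partial dates, and similar in both arms, because pre-treatment events cannot depend on treatment. The expected result is some inflation of TEAE counts in both arms rather than a biased comparison. No efficacy result or hypothesis test is affected.

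**What to change.** In SAP 9.2.5.1, apply the maximum only when the known month and year are those of first IMP (or, for year-only dates, when the known year is), and then impute the date and time of first IMP. Otherwise impute the first day of the known month (or year). Earlier months stay pre-treatment, with the imputed start no earlier than the consent date; without that floor, an event in the month of consent could be dated before AE collection began.

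In SAP 6.9.2.2, adopt the wording of section 2 and the protocol, so that onset on or after the time of first IMP qualifies. State that an AE on the first-dose date with no recorded time is treated as emergent.

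With a first dose on 20-Oct-2022, July and September 2022 then become 01-Jul and 01-Sep (or the consent date, if later) and are not TEAEs. October becomes 20-Oct and November 01-Nov, and both are TEAEs, as the closing sentence intends. A check that no imputed start falls after a recorded end date would catch the remaining case: an event in the first-dose month that ended before dosing.

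The cost is a few sentences in the SAP and a small change to the derivation code. If the flag has already been derived, record which rule was programmed and how many AEs had partial start dates.
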